# Table JPBK.12.1.Rules for Determining Date of Progression or Censor for
Progression-Free Survival

Note: Progression-free survival and associated outcome is determined by the earliest of the dates above, if more than 1 situation applies.

The statistical comparison of PFS between treatment groups will be conducted using the same methods for OS as described in Section 12.2.6.

The objective response rate of each treatment arm will be calculated as defined by RECIST v1.1. All rates will be compared between treatment arms based on a normal approximation for the difference between the rates.

Details of the statistical methods for analyzing efficacy outcomes are described in the SAP.

# 12.2.8. Sensitivity Analysis

Sensitivity analyses may be undertaken for the efficacy endpoints in order to evaluate the robustness of the analysis. The following sensitivity analyses may be performed for PFS:

**Progression-Free Survival Sensitivity Analysis 1** (censoring for receiving subsequent systemic anticancer therapy): if a patient is initiated on another anticancer therapy prior to objective progression, including any postdiscontinuation treatment systemic therapy, radiotherapy, or surgical intervention, PFS will be censored at the date of the last complete objective progression-free disease assessment before initiation of the new therapy, regardless of whether or not this patient subsequently had objective progression or died.

**Progression-Free Survival Sensitivity Analysis 2** (nonobjective progression as a PFS event): if a patient is discontinued from study treatment due to investigator determined non-objective progression (for example, symptomatic deterioration), then the patient's PFS time will be calculated using the date of non-objective progression as the progression date.

**Progression-Free Survival Sensitivity Analysis 3** (back-dating progressions at unscheduled assessments): if a patient has objective progression at an unscheduled disease assessment, then the PFS time for that patient will be back-dated to the prior scheduled disease assessment.

Additional sensitivity analyses may be carried out for patients who are *KRAS* positive based only on central test result. Details are described in the SAP.

# 12.2.9. Pharmacokinetic Analyses

Pharmacokinetics analyses will be conducted on all patients who have received at least 1 dose of abemaciclib and have had samples collected (see PK sampling schedule in Attachment 7).

Mean population PK parameters for abemaciclib in plasma (clearance, exposure, volume of distribution, and half-lives) and inter-individual PK variability will be computed using nonlinear mixed effect modeling (NONMEM). The current PK model for abemaciclib, which has been developed using plasma concentration data available from the Phase 1 Study JPBA, will be updated using the plasma data collected in this study. Covariate effects (such as age, weight, sex, creatinine clearance, and plasma protein levels) on the PK parameters of abemaciclib in plasma will also be investigated.

The mean population PK properties of abemaciclib metabolites LSN2839567, LSN3106726, and LSN3106729 in plasma may also be analyzed by means of NONMEM.

Finally, pharmacodynamic data (such as neutrophil, lymphocytes, or platelets counts in blood) collected in this study may also be analyzed by means of NONMEM and connected to the population PK model in a PK/pharmacodynamic model.

The version of software used for the analysis will be documented and will meet the Lilly requirements of software validation.

# 12.2.10. Biomarker Analyses

### 12.2.10.1. KRAS Mutation Assessment

Concordance (agreement) analysis will be performed on samples with valid *KRAS* status (mutation positive and mutation negative) using both the investigational assay and the reference method (Sanger sequencing). Measures of agreement between the investigational *KRAS* assay and the reference method, including positive percent agreement, negative percent agreement, and overall percent agreement, and their corresponding exact 2-sided 95% CIs, will be estimated for the overall mutation status; that is, mutation detected or not detected for the 7 mutations of *KRAS* gene. A secondary agreement analysis between the investigational *KRAS* assay and the reference method will be performed for each of the tumor tissue sample types (surgical resection, fine needle aspirate and core needle biopsy). The data will also be summarized for each of the 7 *KRAS* mutations separately.

### 12.2.10.2. Other Biomarkers

For other biomarkers relevant to abemaciclib and the disease state, the distributions of biomarkers will be summarized for the patient population for which samples are available.

Associations between clinical endpoints and biomarkers will be evaluated using data from patients who have an evaluable sample for each biomarker of interest, and such evaluation will be done on an individual marker basis.

# 12.2.11. Health Outcome/Quality of Life Analyses

Patient-reported outcomes are measured through paper versions of the following:

- MDASI-LC (includes additional page with 11 items that will be scored separately)
- EQ-5D 5L (EuroQol 5-Dimension 5 Level)

The reason and number of missing and incomplete questionnaires/assessments by visit will be summarized for each instrument and study arm.

#### 12.2.11.1. MDASI-LC

The MDASI-LC population will include all patients who completed at least 1 baseline followed by at least 1 MDASI-LC assessment after 1 cycle of study drug (Cycle 2 Day 1 or later).

The MDASI-LC will be summarized for each assessment period and scored as described (Mendoza et al. 2011). The instrument will be reported as core symptoms (Items 1-13), interference items (Items 14-19) and lung symptoms (Items 14-16), and the 11 additional items will be reported as brain tumor symptoms (Items 23 through 30) and additional 3 items (31-33), as well as each individual item.

For each patient with data from baseline and at least 1 other visit, the maximum change from baseline score will be calculated and summarized for MDASI-LC composite scores, and "worst pain".

Further analysis details will be described in the SAP.

### 12.2.11.2. Health State Utility

The EQ-5D 5L population will include all patients who completed at least 1 baseline followed by at least 1 EQ-5D 5L assessment after 1 dose of study drug.

The EQ-5D 5L data will be scored based on EuroQol recommendations. The index score is calculated from a set of item weights to derive a score of <0 to 1, with 1 representing the best health status. The visual analogue score (VAS) is scored from 0 (worst imaginable health state) through 100 (best imaginable health state) to represent the patient's self-report for each day. EQ-5D 5L responses for each item will be summarized by frequency and corresponding percentages. Descriptive statistics for the index and VAS will be calculated as described in the SAP.

#### 12.2.11.3. Use of Pain Medications

Pain medication will be classified into 1 of 6 categories by the sponsor, using an analgesic ladder approach with medication category based on a World Health Organization scale outlined in Table JPBK.12.2. A therapy category for each cycle will be assigned according to the maximum category of therapy administered based on analgesic data from the Concomitant Form for that cycle. Category of pain medication for each cycle will be determined based on the data collected

on analgesic use by Anatomical Therapeutic Chemical code. Change in categories based on analgesic ladder compared to baseline will be described by arm.

 Table JPBK.12.2.
 World Health Organization Pain Scale

Description
No analgesia
Aspirin (for pain, not cardiovascular prophylaxis), acetaminophen, nonsteroidal anti-inflammatory drugs
Codeine, hydrocodone, pentazocine, oxycodone
Oral morphine, hydromorphone, methadone, transdermal fentanyl
Parenteral opiates
Neurosurgical procedures (blocks)

# 12.2.12. Safety Analyses

All safety summaries and analyses will be based upon the Safety Population as defined in Section 12.2.1.

Overall exposure to study drug, the numbers of patients completing each cycle, and the dose intensity will be summarized using descriptive statistics. The number of patients with dose reductions, dose delays, or dose omissions will also be summarized, as will the reasons for dose adjustments.

AEs will be reported using a unified CTCAE/MedDRA reporting process:

- The CTCAE v4.03 term reported by the investigator will be mapped to the MedDRA Preferred Term (PT) and System Organ Class (SOC) of the corresponding MedDRA Lower Level Term (LLT), unless the reported CTCAE term is 'Other – specify'.
- If the reported CTCAE term is 'Other specify' the MedDRA LLT, PT, and SOC mapped from the verbatim AE term will be used.
- All listings and summaries will use the PT resulting from this process.

Preexisting conditions are defined as adverse events that begin prior to the first dose of study drug. A TEAE is defined as an event that first occurred or worsened in severity between the day of first dose and 30 days after treatment discontinuation (or up to any time if serious and related to study treatment). Comparisons of preexisting conditions to on-treatment events at the LLT level will be used in the treatment-emergent computation.

An overall summary of AEs will be provided for AEs deemed by the investigator to be possibly related to study drug, and repeated for events regardless of study drug causality. Incidence rates of these events will be compared between treatment arms using Chi square test.

The following summaries will be produced by PT within SOC: preexisting conditions, SAEs, TEAEs, drug-related TEAEs, and procedure-related TEAEs.

The following summaries will be produced by PT within SOC and maximum CTCAE grade: laboratory-based TEAEs, nonlaboratory-based TEAEs, drug-related laboratory-based TEAEs, and drug-related nonlaboratory-based TEAEs.

Reasons for death will be summarized separately for on-therapy and within 30 days of treatment discontinuation.

Hospitalizations and transfusions during the study treatment period or during the 30-day short-term follow-up period will be summarized by treatment group.

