# 9.5. Blinding

This is a randomized, open-label study. Randomization will occur using an interactive web response system. Assignment to treatment groups will be determined by a computer-generated random sequence. Each patient in this study will be aware of his or her own assigned treatment group. At each investigative site, all staff involved in treating and caring for study patients will have full knowledge of treatment assignments for the patients under their care.

In order to maintain the scientific integrity of this trial, access to study data will be strictly controlled prior to the interim and final analyses. For the accumulated group-level data, treatment assignment will not be included, and other parameters that can disclose treatment assignment will be scrambled. Therefore, the sponsor and all investigative sites will remain

blinded to treatment group assignments for the summary statistics and reports until the database lock for the final analysis. Scrambled treatment assignments will be used in the reporting database for Lilly trial-level safety review until the final database lock. Interim analyses will be carried out approximately every 6 months by an independent DMC (external to Lilly) to monitor safety and efficacy. The DMC is unblinded and the Statistical Analysis Center (SAC), which is also external to Lilly, will carry out analyses for the DMC. Until the primary analyses, only the SAC and the DMC will be unblinded to the summary statistics and reports.

For the interim PK analysis to occur prior to the interim/primary analyses, the list of individuals that will have access to unblinded data will be provided with the PK/PD analysis plan, and documentation concerning their access to the data will be retained.

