### 10.3.1. Adverse Events

Lilly has standards for reporting AEs that are to be followed regardless of applicable regulatory requirements that may be less stringent. A clinical study AE is any untoward medical event associated with the use of a drug in humans, whether or not it is considered related to that drug.

Lack of drug effect is not an AE in clinical trials, because the purpose of the clinical trial is to establish drug effect.

Any clinically significant findings from electrocardiograms (ECGs; for example, QTc prolongation), labs, vital sign measurements, other procedures, and so on that result in a diagnosis should be reported to Lilly or its designee. All non-clinically significant findings must be documented in the patient record as not clinically significant and therefore will not be documented in the eCRF.

Cases of pregnancy that occur during maternal or paternal exposures to study drug should be reported. Data on fetal outcome and breast-feeding are collected for regulatory reporting and drug safety evaluation.

Study site personnel will record the occurrence and nature of each patient's preexisting conditions, including clinically significant signs and symptoms of the disease under treatment in the study. All non-clinically significant findings must be documented in the patient record as not clinically significant and therefore will not be documented in the eCRF.

After the study ICF is signed, site personnel will record the occurrence and nature of any AEs and any change in the preexisting condition(s). All AEs related to protocol procedures are reported to Lilly or its designee.

In addition, all AEs occurring after the patient receives the first dose of study drug must be reported to Lilly or its designee via eCRF.

Investigators will be instructed to report to Lilly or its designee their assessment of the potential relatedness of each AE to protocol procedure or study drug via eCRF.

The investigator will decide whether he or she interprets the observed AEs as related to disease, to the study drug, study procedure, or other concomitant treatment or pathologies. To assess the relationship of the AE to the study drug or procedure, the following terminologies are defined:

- **Probably related**: a direct cause and effect relationship between the study treatment and the AE is likely

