- **Possibly related**: a cause and effect relationship between the study treatment and the AE has not been demonstrated at this time and is not probable, but is also not impossible
- Does not know: the investigator cannot determine
- Not related: without question, the AE is definitely not associated with the study treatment

The investigator should classify all "probably related," "possibly related," or "does not know" AEs and SAEs as related to study drug/study procedure.

Patients will be evaluated for AEs at each visit and will be instructed to call their physician to report any AEs between visits.

The National Cancer Institute (NCI) Common Terminology Criteria for Adverse Events (CTCAE) v4.03 will serve as the reference document for choosing appropriate terminology for, and grading the severity of, all AEs and other symptoms. For AEs without matching terminology within the NCI-CTCAE v 4.03 criteria, the investigator will be responsible for selecting the appropriate system organ class and assessing severity grade based on the intensity of the event.

In addition to collecting the AE verbatim and the CTCAE severity grade, AE verbatim text will also be mapped by Lilly or its designee to corresponding terminology within the Medical Dictionary for Regulatory Activities (MedDRA) dictionary.

If a patient's dosage is reduced or treatment is discontinued as a result of an AE, study site personnel must clearly report to Lilly or its designee via eCRF the circumstances and data leading to any such dosage reduction or discontinuation of treatment.

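### The chi-square comparison of investigator-judged drug-related AEs mixes event incidence with open-label attribution to a different drug in each arm; test AEs regardless of causality and report related AEs descriptively

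*Protocol*

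**What the plan says.** Protocol Section 12.2.12 (Safety Analyses) plans an overall summary for "AEs deemed by the investigator to be possibly related to study drug, and repeated for events regardless of study drug causality". The next sentence reads: "Incidence rates of these events will be compared between treatment arms using Chi square test". That sentence covers both sets of events, and the synopsis repeats the same plan. Section 12.2.1 sets tests of treatment effects at two-sided 0.05 unless otherwise stated.

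Relatedness is a judgement made at the site. Section 10.3.1 says: "The investigator will decide whether he or she interprets the observed AEs as related to disease, to the study drug, study procedure", or to other causes. The threshold is low. An event rated "Possibly related" is one where a causal link "is not probable, but is also not impossible", and events rated probably related, possibly related or unknown are all to be classified as related. Section 9.5 states that "all staff involved in treating and caring for study patients will have full knowledge of treatment assignments for the patients under their care". SAP Section 6.2.3 defines study drug as abemaciclib or erlotinib.

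SAP Section 6.2.14.2 tabulates treatment-emergent AEs (TEAEs) and SAEs and repeats the summaries for related ones. It names no between-arm AE test, but it does not withdraw the protocol's test.

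**The concern.** Safety and tolerability is a secondary objective to be compared between the arms (Protocol Section 6.2), so the natural null hypothesis is equal AE risk. The chi-square on related AEs tests a different null: that risk multiplied by the probability of attribution is equal. Randomization does not balance the second factor. Attribution is made after treatment starts, with the arm known, and it concerns an investigational drug in one arm and a marketed drug with a known toxicity profile in the other.

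A significant result could therefore reflect only how readily each drug is held responsible. The reverse is also possible: attribution could offset a real difference in incidence. The related-AE p-value would stand next to the all-causality p-value, and neither document says how to read a disagreement between them.

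**Working it through.** **Inputs from the documents.** About 270 and 180 patients (3:2, Protocol Section 12.1), taken as the safety population on the assumption that every randomized patient is dosed. Pearson chi-square (Section 12.2.12), two-sided 0.05 (Section 12.2.1). The plan states no AE rate, attribution rate or error rate for this test, so there is no figure of its own to reproduce.

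**Assumed inputs.** True AE incidence p, equal in both arms, and attribution probabilities a₁ (abemaciclib) and a₂ (erlotinib). Neither is in the documents, so ranges are shown.

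**Step 1: one attribution per patient.** This fits a single-event row or a rare category. Related incidence in arm i is rᵢ = p × aᵢ. The test rejects when (r̂₁ − r̂₂)² / [r̄(1 − r̄)(1/270 + 1/180)] exceeds 3.84, the upper 5% point on 1 degree of freedom. Exact enumeration of the two binomials gives these rejection rates:

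| Attribution | p = 30% | p = 60% | p = 90% |
|---|---|---|---|
| 80% vs 80% | 5% | 5% | 5% |
| 80% vs 75% | 6% | 10% | 18% |
| 80% vs 70% | 11% | 24% | 52% |
| 80% vs 60% | 33% | 72% | 97% |

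Hand check of the 52%: r₁ = 0.9 × 0.8 = 0.72 and r₂ = 0.9 × 0.7 = 0.63, a difference of 0.09. The pooled rate is (194.4 + 113.4)/450 = 0.684, so the null standard error is √(0.684 × 0.316 × (1/270 + 1/180)) = 0.0447. The rejection limit is 1.96 × 0.0447 = 0.0877. The alternative standard error is √(0.72 × 0.28/270 + 0.63 × 0.37/180) = 0.0452. Power is Φ((0.09 − 0.0877)/0.0452) = Φ(0.05), about 52%.

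Reversing the arms (70% vs 80%) gives 12%, 24% and 51%, so the direction of the gap matters little.

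**Step 2: any related AE, several AEs per patient.** The chi-square sentence follows the overall AE summary. If that summary counts patients with at least one related event, a patient with k independently attributed AEs counts when any one is judged related, so rᵢ = p × [1 − (1 − aᵢ)ᵏ]. At p = 90%:

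| Attribution | k = 3: r₁, r₂ | Rejects | k = 5: r₁, r₂ | Rejects |
|---|---|---|---|---|
| 80% vs 70% | 0.893, 0.876 | 9% | 0.900, 0.898 | 5% |
| 80% vs 60% | 0.893, 0.842 | 35% | 0.900, 0.891 | 6% |
| 50% vs 40% | 0.788, 0.706 | 51% | 0.872, 0.830 | 24% |

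At high attribution rates nearly every patient with an AE has at least one related AE, and the gap closes. At lower rates it does not.

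**Step 3: masking.** Take true incidence of 60% vs 45% and attribution of 60% vs 80%, one attribution per patient. Related incidence is 0.60 × 0.60 = 0.36 and 0.45 × 0.80 = 0.36. The all-causality test rejects in 88% of trials and the related-AE test in 5%.

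**Step 4: the all-causality test.** With equal true incidence it rejects in about 5% of trials at each of the three incidences in Step 1, provided that the events are captured in the same way in both arms.

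**The case against.** The strongest reply is that little depends on this test. The same sentence already requires the all-causality comparison. The SAP, which carries the analysis detail, names no between-arm AE test. OS is the sole primary endpoint, safety stopping has no prespecified rule, and no threshold is tied to a related-AE p-value. All of this stands, and it limits the point to one of interpretation. It does not make the related-AE p-value a test of equal AE risk, and it leaves open whether that test will be run.

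Drug-attributed toxicity is also a legitimate quantity to report, and the dose-adjustment rules in Section 9.4.2.2 refer to it. That supports keeping the counts by arm but does not support a between-arm test. A low threshold for relatedness may also push attribution towards 100% in both arms and narrow the gap. That is possible, and the documents do not settle it.

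A reader might make two stronger inferences that the documents do not support:

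- *The all-causality test is free of attribution.* It is not wholly so. Sections 12.2.12 (Protocol) and 6.2.14.2 (SAP) admit events later than 30 days after discontinuation as treatment-emergent only if they are serious and related. Protocol Table JPBK.10.1 collects only related SAEs in long-term follow-up. Section 10.3.1.1 has SAEs due to progression reported only if judged possibly related. Most on-treatment AEs are untouched by these rules, but the set is not clean.
- *Rejection rates of 52% or 97% apply to the planned overall summary.* Those figures assume one event and one attribution per patient. With several AEs per patient, the same attribution gaps give 9% and 35% (three AEs) or 5% and 6% (five AEs).

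**Conclusion.** The point holds as a minor one. The protocol plans a between-arm test whose null is equality of incidence times attribution, with attribution made open-label and about a different drug in each arm. The test can reject with equal AE risk, or miss a real difference, because of attribution alone.

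The size cannot be fixed from the documents. On the assumed rates it runs from negligible (5% to 6% rejection) to very large (97%), depending on the attribution gap, the incidence and the number of AEs per patient. The calculation further assumes that all randomized patients are dosed and, in Step 2, that AEs within a patient are attributed independently. The documents do not show that attribution will differ, only that nothing in the design prevents it. The all-causality comparison depends much less on attribution, and the OS analysis and its alpha are not affected.

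**What to change.** In Protocol Section 12.2.12 and the synopsis, or by a SAP clarification (which Section 12.2.1 allows before the aggregate database is unblinded), limit the between-arm AE test to events regardless of causality and summarize related events by arm without a p-value. Suggested text: *The incidence of AEs regardless of causality, with onset or worsening from first dose to 30 days after treatment discontinuation, will be compared between arms. AEs judged related to study drug will be summarized by arm without formal comparison.*

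Defining the tested set by that window leaves out the extension for late serious related events, which can still be listed separately. The rule on reporting SAEs due to progression would remain a small residual dependence on attribution, and the report should say so.

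The cost is one or two sentences and the loss of a p-value on related AEs. The counts and the SAP's related-event tables stay as planned.
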